To evaluate the impact of the SPARC intervention on sustained receipt of evidence-based alcohol-related care, we are conducting a pragmatic stepped-wedge trial in 22 KPWA PC clinics (Fig. 3). A stepped-wedge approach [68] was chosen so that all clinics would eventually receive the intervention and because providing practice coaches for more than four clinics at a time was not feasible. The trial has seven waves staggered by 4 months, such that the final 2 months of the active implementation phase of one wave overlaps with the preparation phase of the next wave. The sample for the study is patients 18 years of age and older who have a PC visit in one of the 22 participating clinics during the study period.

Fig. 3

SPARC stepped-wedge pragmatic clinical trial design. *Usual care start: January 1, 2015. **Data collection end date: July 31, 2018. Twenty-two clinics (with three paired to create 19 randomized clinical sites total) were randomized across seven waves with stratification (three waves year 1 and four waves years 2–3). Clinics in square bracket are paired as one site.

Randomization

Stratified randomization was used, with 9 clinics randomized in year 1 (three sites in each of three waves), and the remaining 13 clinics randomized in years 2–3 (Fig. 3). Clinics randomized in year 1 are referred to as Y1 sites and those randomized in years 2–3 as Y2 sites. The random assignment to study wave within Y1 and Y2 was generated using a computer-generated list of random numbers by the study biostatistician after all sites were recruited. An additional file describes our randomization scheme and rationale in detail [see Additional file 1].

Four phases of the SPARC trial

Figure 2 shows the four phases of implementation in each clinic. As above, each clinic has approximately 6 months of support from practice coaches, including up to 8 weeks in the “preparation” phase, before the official launch date of SPARC/Behavioral Health Integration,

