Samples and time intervals. A population-based denominator is used in all analyses as the least-biased denominator because clinical site implementation of the SPARC and Behavioral Health Integration interventions is expected to change the proportion and characteristics of patients screened, the proportion who screen positive for unhealthy alcohol use, and the proportion and characteristics of those diagnosed with AUDs. Unless otherwise specified, the sample for each measure is the set of patients who have a PC visit to a PC clinical site for any reason during each

time interval used in analyses. Time intervals used in analyses are typically 4 weeks (i.e., 28-day intervals before and after each clinic's specified launch date). This interval is selected to provide adequate numbers of outcomes per interval [62]. Specifically, primary analyses will compare the monthly (28-day) proportion of patients with each outcome in the pre- versus post-implementation periods.

Statistical analysis

Main analyses of the trial compare two primary outcomes—alcohol SBI and AUD treatment—among PC patients seen in the participating PC clinics before and after the randomized SPARC launch (Fig. 2 and Table 4). Primary analyses will compare the monthly outcome rates of the two primary outcomes before and after launch. Secondary analyses will also compare primary outcomes across other study phases (Fig. 2 and Table 4).

Table 4 The primary analysis

Primary analyses compare months before vs. months after the assigned launch date (usual care + preparation phases vs. active implementation + sustainment phases).
Secondary analyses
a. Usual care vs. active implementation
b. Usual care vs. sustainment
c. Active implementation vs. sustainment

Analyses will follow the general framework for analyzing data from a stepped-wedge trial [70, 71]. The intervals used in analyses are 28-day periods (“month” hereafter) before and after the launch date for each clinic. Specifically, we will model indicator variables for the primary outcomes monthly (e.g., indicator for whether each patient who had a PC visit that month received alcohol SBI or a new AUD diagnosis and treatment) using the following logistic mixed-effect model:

$$\text{logit } P(Y_{ijm} = 1) = \alpha + \beta Int_{jm} + \gamma S_j + f(cm) + b_j + u_i,$$

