where Y_{ijm} is the outcome for person i who visited site j in month m . The term Int_{jm} is an indicator variable for whether the visit month was before or after the randomly assigned SPARC launch date for that site (i.e., if the site was in the usual care or preparation vs. active implementation or sustainment phases; Fig. 1 and Table 4). Following intention-to-treat principles, unless otherwise specified, phases will be defined based on official randomized launch dates, when active implementation was planned to start, rather than the actual date when the site began implementing SPARC (if implementation was delayed). The term S_j is an indicator for whether site j was a Y2 versus a Y1 site (stratification variable), which accounts for possible differences in outcomes across these two groups of sites, and $f(cm)$ is a pre-specified function of calendar month of the study when the PC visit occurred (1–31) to account for the potential for a secular trend in the outcome rates over time (January 2015–July 2018). We plan to model $f(cm)$ using indicator variables for seven 4-month periods.

Additionally, $u_i \sim N(0, \tau_u^2)$ and $b_j \sim N(0, \tau_b^2)$ are person- and site-level random intercepts to account for correlation of outcomes from the same individual over multiple months and of individuals from the same site, respectively. The primary analysis (Table 4) will be a two-sided Wald test (at the 0.05 level) of the coefficient β , which denotes the log odds ratio comparing the monthly outcome rate in the post period to the monthly outcome rate in the pre-period. We will also calculate 95% Wald confidence intervals (95% CI) for β . Secondary analyses of changes across all four phases will be accomplished by replacing the Int_{jm} term with a categorical variable for whether the month of the PC visit was in the usual care, active implementation, or sustainment phase and for testing the relevant contrast.

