Secondary analyses, parallel to the primary analyses, will assess each intermediate outcome, as explanatory analyses, in the pre- versus post-implementation periods. If increases in alcohol screening and AUD assessment (Table 3) are observed, secondary patient-level analyses will evaluate whether screening is associated with increased brief interventions, and whether completing an Alcohol Symptom Checklist is associated with increased new AUD diagnoses. Additional secondary analyses and sensitivity analyses are described in an additional file [see Additional file 1].

Statistical power

With 19 sites, seven study waves (with number of sites per wave described above), and 4 months between launch dates across waves, and assuming an average of 1205 patients seen per site per month (based on baseline data obtained at the time of the grant proposal for the trial), we will have 80% (90%) power to detect an increase in brief intervention rates of 7.1 (8.2) per 10,000 patients seen and an increase in treatment engagement of 2.6 (3.1) per 10,000 patients seen. Calculations, which were based on a two-sided test and a type 1 error rate of 0.05 and used the method of Hussey and Hughes (2007), assumed the following usual care rates for the main study outcomes: 34.2 per 10,000 patients seen for the brief intervention outcome (BI; $0.342\% = 19\% \text{ screened} \times 36\% \text{ screened positive} \times 5\% \text{ brief intervention}$) and 3.9 per 10,000 for treatment initiation and engagement ($0.039\% = 1.26\% \text{ newly diagnosed} \times 37.5\% \text{ initiating treatment} \times 8.2\% \text{ engaged}$). We further assumed a value for the intraclass correlation coefficient of 0.001, based on baseline data from the included sites.

Qualitative evaluation

Data collection

Several sources of qualitative data are routinely collected during the trial. Detailed typed minutes are taken during weekly operations meetings. In addition, detailed typed notes are taken of discussions during weekly formative evaluation meetings, using a spreadsheet to document the meeting date, clinic site, and a summary of practice coaches' descriptions of the current state of implementation at that site, including barriers and facilitators and any resulting implementation adaptations. All names are omitted from notes to protect confidentiality (only clinical roles are recorded).

Qualitative analyses

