### Outcome measures and time frames

The main primary and secondary outcome measures, as described in the Protocol Paper, are defined in **Table 2** below. Indicator variables for each outcome are created at the level of the primary care visit (since a patient may have multiple primary care visits during the study period). Measures are then aggregated into time-intervals (e.g., weekly or monthly). For the primary analysis, measures are aggregated into 28-day intervals (hereafter referred to as “months”), defined relative to the official launch date of SPARC within the clinic (denoted by T0). For example, the co-primary alcohol brief intervention measure aggregated at the monthly level is defined as the proportion of patients seen in the month who had a brief intervention (defined in **Table 2**) at any point during that month.

**Table 2.** SPARC Trial Primary, Secondary and Other Outcomes from EHR and Claims Data

Category	Measure	Description
Primary Outcomes		

Prevention	Alcohol Brief Intervention	Indicator for whether a patient had a brief intervention documented in the EHR* on the day of, or in the 14 days following a PC visit, and had a positive alcohol screen on the day of the visit or in the prior 365 days*
Treatment	Treatment for Newly Diagnosed AUD (NCQA 2017 alcohol and drug treatment measure)	Indicator for whether a patient had a new AUD diagnosis* and initiated and engaged in AUD treatment*
Intermediate Outcomes		
Prevention	Alcohol screening documented	Indicator for whether a patient had AUDIT-C screening documented in the EHR on the day of the visit or in the prior 365 days
Prevention	Positive alcohol screen	Indicator for whether a patient screened positive on the AUDIT-C (3–12 women and 4–12 men), on the most recent screen documented on the day of the visit or in the prior 365 days
Prevention	High positive alcohol screen	Indicator for whether a patient had a high-positive AUDIT-C score (7–12 points), on the most recent screen documented on the day of the visit or in the prior 365 days
Assessment	Assessed for DSM-5 AUD symptoms	Indicator for whether a patient with a high-positive screen in the past year completed an AUD Symptom Checklist on the day of the visit or in the prior 365 days
Identification	Past-year AUD diagnosis	Indicator for whether a patient had an AUD diagnosis defined as an ICD code for an AUD diagnosis per NCQA anywhere in or outside KPWA (e.g. includes claims) on the day of the PC visit or in the prior 365 days

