### Primary analysis

Following the general framework for analyzing data from a stepped-wedge trial (Hussey and Hughes 2007; Hughes et al. 2015), for each outcome described above we will apply the following logistic mixed-effect model (GLMM),

$$\text{logit } P(Y_{ijm} = 1) = \alpha + \beta \text{Int}_{jm} + \gamma S_j + f(cm) + b_j + u_i,$$

where  $Y_{ijm}$  is the outcome for person  $i$  who visited site  $j$  in time interval  $m$ . As described above, the intervals used in analyses are 28-day periods ("months" hereafter) before and after the launch date for each clinic. The term  $\text{Int}_{jm}$  is an indicator variable for whether site  $j$  was in the post- versus pre-implementation period as of that month. The term  $S_j$  is an indicator for whether site  $j$  was a Y2 site versus a Y1 site (stratification variable), which accounts for possible differences in the outcome across these two years of sites (Y1 and Y2), and  $f(cm)$  is a pre-specified function of calendar month to account for the potential for a secular trend in outcome rates over time. We plan to model  $f(cm)$  using indicator variables for each 4-month calendar period. Alternate specifications will be considered in a sensitivity analysis (details below). Additionally,  $b_j \sim N(0, \tau_b^2)$  is a site-level random effect to account for correlation of individuals from the same site and  $u_i \sim N(0, \tau_u^2)$  is a person-level random effect to account for correlation of outcomes from the same individual, since a person can have a visit at multiple sites in the same or different month, or at the same site over multiple months.

The primary comparison (1) described above will be evaluated by first conducting a two-sided Wald test (at the 0.05 level) of the coefficient  $\beta$ . Ninety-five percent Wald confidence intervals (95% CI) for  $\beta$  will also be calculated.

For descriptive purposes, from the model, we will estimate the marginal predicted probability of the outcome in the pre- and post-implementation period by averaging over covariate distribution and the random effects.

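### Does the month index of 1–31, with seven four-month periods against a 43-month study, leave the primary model's calendar-time term undefined?

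*Protocol*

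**What the plan says.** **Protocol, Statistical analysis.** The calendar-time term f(cm) depends on the "calendar month of the study when the PC visit occurred (1–31") and is there to absorb any "secular trend in the outcome rates over time (January 2015–July 2018"). It is to be coded with "indicator variables for seven 4-month periods".

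**Protocol, Fig. 3 caption, and SAP, Study sample.** Both give 1 January 2015 and 31 July 2018 as the ends of the study; the caption reads "Usual care start: January 1, 2015".

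**SAP, Primary analysis.** The same term is to be modelled "using indicator variables for each 4-month calendar period". Alternative codings are promised as a sensitivity analysis.

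**Analysis interval.** This is separate from f(cm). The Protocol says "The intervals used in analyses are 28-day periods", counted from each clinic's launch, and the SAP agrees: "For the primary analysis, measures are aggregated into 28-day intervals".

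**Protocol, Statistical power.** The calculation assumes seven waves with "4 months between launch dates across waves".

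The supplied text of neither document dates the four-month periods or names a reference period.

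**The concern.** In a stepped wedge the share of sites that have launched rises with calendar time, so the intervention coefficient β is only as trustworthy as the time adjustment beside it. Here one sentence gives two lengths for the time axis (31 and 43 months), and the two documents describe the coding differently (seven periods, or as many as the span holds). If seven were taken as a total, some long stretch of months would share one time level. A trend inside a stretch during which sites are crossing over would then be credited to the intervention. If 1–31 were taken literally, a year of pre-launch data might be dropped. Because launch-anchored 28-day intervals do not line up with calendar blocks, it also seems unclear which block an interval belongs to. Both primary outcomes are tested through β, so the matter deserves a check.

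**Working it through.** **1. Month count.** January 2015 to July 2018 is 3 × 12 + 7 = 43 calendar months (1,308 days; 1,308/28 = 46.7 intervals). The 31 is reproduced on neither scale. It equals January 2016 to July 2018: 2 × 12 + 7 = 31. Four-month periods needed: 43/4 = 10.75, so 11; or 31/4 = 7.75, so 8. Seven periods cover 7 × 4 = 28 months, exactly April 2016 to July 2018, and 43 − 28 = 15 months come before. The first launch in SAP Table 1 is 4 April 2016, so those 15 months are entirely pre-launch at every site.

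**2. The plan's power figures.** Hussey–Hughes variance by generalised least squares, with waves of 3, 3, 3, 3, 3, 2, 2 sites, one baseline plus seven periods, 4 × 1,205 = 4,820 patients per site-period and ICC 0.001. With σ² = p̄(1 − p̄) at the mean of the two rates and τ² = σ² × ICC/(1 − ICC), the covariance of a site's period means is τ²J + (σ²/4,820)I.

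| Outcome | Increase per 10,000 | Stated power | Recomputed |
|---|---|---|---|
| Brief intervention | 6 / 8 / 10 | 0.67 / 0.89 / 0.97 | 0.668 / 0.883 / 0.973 |
| Brief intervention | 7.1 / 8.2 | 0.80 / 0.90 | 0.803 / 0.897 |
| AUD treatment | 2 / 3 / 4 | 0.60 / 0.89 / 0.98 | 0.593 / 0.880 / 0.979 |
| AUD treatment | 2.6 / 3.1 | 0.80 / 0.90 | 0.791 / 0.897 |

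The figures reproduce to within about one point. A monthly layout with launches four months apart and the Y1/Y2 stratum term gives, at 7.1 and 8.2 per 10,000, power of 0.806 and 0.899 with eight periods from January 2016, and 0.871 and 0.944 with 11 periods over 43 months. The longer span can only help.

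**3. Trend left in β.** Site-by-day least squares on the linear scale: 19 sites, Table 1 launch dates, 1,205 patients per site-month, ICC 0.001, stratum term included. The data are given no intervention effect and a drift of 1 unit per month. The fitted coefficient on the intervention indicator is then the number of months of trend that leaks into β.

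| Coding of f(cm) | Months of trend in β | SE relative to first row |
|---|---|---|
| SAP rule: 11 periods from January 2015 | 0.284 | 1.000 |
| 15-month reference, then seven periods | 0.342 | 0.997 |
| 11 periods cut so that one starts in April 2016 | 0.342 | 0.997 |
| Eight periods, data from January 2016 | 0.340 | 1.093 |
| Seven groups, first runs to July 2016 | 1.739 | 0.986 |
| Seven from January 2015, last 15 months as one block | 2.689 | 0.962 |
| Seven from January 2015, last 15 months pooled into the seventh | 5.319 | 0.907 |

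Rows two and three agree because no site launches before April 2016. Splitting or pooling those months affects all sites alike and cannot mimic an intervention effect.

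**4. Size against the design effect.** Detectable log odds ratios at 80% power: brief intervention, 41.3 against 34.2 per 10,000, 0.189; AUD treatment, 6.5 against 3.9, 0.511. Standard errors are these divided by 2.80: 0.0676 and 0.1825. The documents give no trend, so assume 0.01 to 0.05 log-odds per month, a factor of exp(0.01 × 42) = 1.5 to exp(0.05 × 42) = 8.2 from first month to last.

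- SAP rule, brief intervention: 0.284 × 0.01/0.189 = 1.5% to 0.284 × 0.05/0.189 = 7.5% of the detectable effect. AUD treatment: 0.6% to 2.8%.
- Reference plus seven, brief intervention: 1.8% to 9.0%. AUD treatment: 0.7% to 3.4%.
- Worst of these: bias/SE = 0.0171/0.0676 = 0.25, which takes a two-sided 5% test to 5.7%.

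**5. Which block an observation belongs to.** The Protocol ties f(cm) to the month of the visit, the model is at person level, and the SAP builds outcome indicators per visit. The time level therefore follows the visit date, whatever 28-day interval the visit falls in. Only a patient with several visits in one interval, on both sides of a block boundary, is left unaddressed.

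**The case for a change.** The strongest case for amending is that a term described as pre-specified should be reproducible from the text, and this one is not quite. The index contradicts the dates beside it. It could be repaired in two ways (1–43, or a trend window starting in January 2016), and the second would raise the standard error by about 9%. Read without the SAP, the Protocol's seven even permits codings that leave 1.7 to 5.3 months of trend. Writing down the boundaries would cost almost nothing. The details of the promised alternative codings are not in the supplied SAP text, although they may be in material not available here, such as the Protocol's additional file.

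The inconsistency itself stands. The inference that the primary result is at risk does not. The SAP gives every four-month period its own indicator, which excludes the codings with long pooled stretches after launches begin. SAP Study sample places 2015 in the base population, so dropping that year is not the natural reading; if it were dropped, the stated power would still hold. The lack of a named reference is not a separate fault: once the grouping of months is fixed, the choice of reference category does not alter β. A four-month grid starting in February or March leaves 0.53 or 0.60 month, and at the extreme drift the latter takes type I error for brief intervention to about 7%. A study that starts on 1 January and speaks of calendar periods gives no reason to choose such a grid.

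**Conclusion.** No change to the plan follows. The 1–31 index is a clerical slip, and the undated periods are a detail that an analyst following the SAP would fill soundly. The SAP rule and the natural reading of the Protocol's seven differ by 0.342 − 0.284 = 0.06 month of trend and by 0.3% in standard error. Under either, bias is at most 9% of the detectable brief-intervention effect, and that only at an eight-fold drift over the study; type I error stays within 5.0–5.7%, and the stated power is unaffected. Writing out the boundaries would make the text tidier without materially changing a result.

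This rests on a linear-scale approximation with a linear trend common to all sites, the Table 1 dates, ICC 0.001 and an assumed range of drift. Person-level effects were not modelled. It also assumes that the analysis follows the SAP wording over the full 43 months.

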# Statistical Analysis Plan for SPARC Trial

## Background

Alcohol use is a major cause of disability and death worldwide. To improve prevention and treatment addressing unhealthy alcohol use, experts recommend that alcohol-related care be integrated into primary care (PC). However, few healthcare systems do so. To address this gap, implementation researchers and clinical leaders at Kaiser Permanente Washington (KPWA) partnered to design a high-quality Program of Sustained Patient-centered Alcohol-related Care (SPARC).

The study aim is to evaluate the effectiveness of the SPARC implementation at improving alcohol-related care within 22 KPWA clinics as part of a stepped-wedge randomized implementation trial. Specifically, our primary objectives are to evaluate whether the SPARC implementation intervention increased (1) brief interventions for unhealthy alcohol use, and (2) initiation and engagement in treatment of alcohol use disorders (AUDs). Details on the specific components of the SPARC implementation are in the protocol paper (Glass et al. 2018).

Trial registration: [NCT02675777](https://clinicaltrials.gov/ct2/show/NCT02675777)

## Stepped-wedge trial design

To evaluate the effectiveness of the SPARC implementation, we are conducting a pragmatic stepped wedge trial in 22 KPWA clinics. The trial design (**Figure 1**) addressed several practical concerns of the health system while maintaining a rigorous evaluation of SPARC. The 22 clinics were randomized into 7 mutually exclusive groups of clinics (referred to as “waves”). Here we briefly summarize the features of the design; more detailed explanations for these requirements are described in the protocol paper (Glass et al. 2018):

- A few pairs of clinics were clustered together into larger single clinical sites for the purpose of receiving the SPARC implementation. This resulted in 19 distinct clinical sites, hereafter referred to as “sites.”
- The health system provided input on implementation timing by conducting a stratified randomization on the year of the implementation; the health system identified 9 sites that would be randomized in Year 1 (3 sites in each of 3 waves), and the remaining 10 sites that would be randomized in Years 2-3 (in two waves of 3 sites each and two waves of 2 sites each). We will refer to sites randomized in Year 1 as Y1 sites and sites randomized in Years 2-3 as Y2 sites.
- It was desired that one of the Y2 sites be in a wave with just a single other site
- It was desired that the final wave consist of only 2 sites.

For each wave, there was a 2-month preparatory period prior to the “launch date” of the 4-month period of active implementation. The “launch date” was specified at the time of randomization to study

		Intervention time point								
		Wave	0	1	2	3	4	5	6	7
Y1	1									
	2									
	3									
	4									
	5									
	6									
	7									

**Figure 1:** Schematic illustrating the stepped wedge design, in which 19 sites were divided into 7 waves (2-3 sites per wave) and stratified across two groups (Y1 and Y2). Gray squares denote time periods in which the SPARC implementation was to be implemented based on randomization, which includes the active implementation period and the sustainment period (defined below).

wave. It was the date when each site was intended to start Behavioral Health Integration screening for all patients who came to the site.

